16.2.3. Planned subgroup analyses

No sub-group analyses are planned.

16.2.4. Missing data and sensitivity analyses

For the primary outcome, where patients are missing the primary outcome (for example due to non-attendance at 6-month visit), they shall be treated as a failure and included in the denominator only and thus no imputation of missing data is planned.

An analogous strategy for binary secondary outcomes will be used.

For continuous, or pseudo-continuous secondary outcomes with only one post baseline time-point of collection, no imputation will be performed and the number of participants missing the relevant outcome data reported.

For continuous, or pseudo-continuous secondary outcomes with more than one post-baseline time-point of collection, the above-described modelling approach will implicitly impute observations using patient-within-arm imputations methods suitable for longitudinal data imputation.

Full details will be included in the Statistical Analysis Plan.

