8.1.2. Secondary outcomes

All secondary outcomes measured at 6 months post-randomisation unless stated otherwise:

- Clinical outcomes:
 - Change in papilloedema as measured by OCT
 - Headache: Monthly headache days (MHD), Monthly migraine days, Headache responder rate ($\geq 50\%$ reduction in MHD), Monthly analgesic days and Monthly headache severity (numerical rating scale lowest 0-10 highest).
 - Headache disability (using the Headache Impact Test-6 (HIT-6))

- Weight and BMI
- Patient-centred outcomes:
 - Quality of Life (QoL) measured using the 36-item short form survey (SF-36) summary score, physical component score and mental component score
 - QoL measured using the EQ-5D-5L
 - Vision related QoL measured using the National Eye Institute Visual Function Questionnaire-25 (NEI-VFQ-25) plus the 10-item supplement
 - Binge eating measured using the Binge Eating Scale (BES)
 - Alcohol use measured using the Alcohol Use Disorders Identification Test (AUDIT)
 - Anxiety and depression measured using the Hospital Anxiety and Depression Scale (HADS)
 - Tolerability of weight loss in IIH driven by Tirzepatide as determined by all cause discontinuation at 6, 12 and 18 months
- Service use outcomes:
 - Service use (doctor attendance, hospital attendance, days in hospital, lumbar punctures, brain imaging scans) (as recorded by Client Service Receipt Inventory (CSRI))
 - Medication use (use and dose of acetazolamide or other ICP lowering drugs)
 - Absenteeism and presenteeism measured using the Work Productivity and Activity Impairment (WPAI) Scale

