8.2.4. Headache responder rate

Headache responder rate ($\geq 50\%$ reduction in MHD from baseline) is the proportion of participants achieving at least 50% reduction in the number of MHD. This is clinically relevant as it is used as an empirical review for continuing or discontinuing headache therapy⁶⁴. As a sensitivity analysis, we will appraise the proportion of participants achieving at least a 30% reduction in the number of MHD.

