Informed consent is defined as the process of learning key facts about a clinical trial before deciding whether or not to participate. It is a continuous and dynamic process and participants should be asked about their ongoing willingness to continue participation at all visits. Participants should be aware from the beginning that they can freely withdraw (cease to participate) from the trial at any time. A participant may wish to cease to participate in a particular aspect of the trial. The changes in levels of participation within the trial are categorised in the following ways:

No trial intervention: The participant would no longer like to receive the trial intervention, but is willing to be followed up in accordance with the schedule of assessments and if applicable using any central UK NHS bodies for long-term outcomes (i.e. the participant has agreed that data can be collected and used in the trial analysis).

No further data collection: The participant is not willing to be followed up in any way for the purposes of the trial AND does not wish for any further data to be collected (i.e. only data collected prior to any changes of levels in participation can be used in the trial analysis).

The details of changes of levels in participation within trial (date, reason and category of status change) will be entered onto the Participant Change of Status Form on the EDC. Participants can change their level of participation without giving a reason.

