16.2.1. Primary outcome

Resolution of papilloedema at the 6 month assessment. Where patients are missing the primary outcome (for example due to non-attendance at 6-month visit), they shall be treated as a failure and included in the denominator only (unless there is data from an unscheduled visits which could be utilised).

Resolution of papilloedema will be reported as n/N where n is the number of participants with resolution of papilloedema and N the total number of participants in the corresponding trial arm, and percentages as appropriate. Logistic regression model will be used to analyse the primary outcome. Risk ratio, risk difference and the associated 95% confidence intervals will then be derived using marginal standardisation method.

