16.2.2. Secondary outcomes

Binary outcomes will be compared using an analogous method to that described under the primary outcome.

Non-ophthalmologic continuous, or pseudo-continuous outcomes collected only once post-baseline will be displayed as change from baseline and will be analysed using a linear regression model adjusted for baseline where appropriate. Results will be presented as adjusted mean differences with 95% confidence intervals. Statistical significance of a difference between treatment arms will be assessed based on the model.

Non-ophthalmologic continuous, or pseudo-continuous outcomes where the outcome is collected at multiple timepoints post-baseline (including patient reported outcome measures) will be assessed for differences between arms using mixed effect repeated measures models using linear patient trajectories through time (alternative analytical functions of time may be considered as necessary). In the initial model, a treatment by time interaction effect will be included in the model. If this is not significant, it will be considered that the treatment effect is constant over time, and models without the treatment by time interaction term will be fitted. Results will be presented as adjusted mean differences and 95% confidence intervals.

Ophthalmologic continuous, or pseudo-continuous outcomes (OCT outcomes) may have data collected in more than one eye. To best use this and increase statistical efficiency while accounting for the non-independence and high correlation between eyes within individuals, we will use hierarchical models to nest observations within patients. These models will have adjustments for treatment allocation and group-level effects for the effect of eye within participant. The presence of a linear predictor and slope-varying terms will be dependent on the number of post-baseline observations. The presence of a treatment effects will also be tested by a likelihood ratio test against a nested model with no treatment variable and otherwise identical model specification.

Ordinal outcomes will be analysed akin to the continuous outcomes however will be compared between treatment arms using ordered logistic regression models.

Data pertaining to exploratory outcomes will be summarised descriptively and/or graphically using methods appropriate to the data type. Exploratory outcomes will be presented separately for each of the (randomisation) questions (R2a, R2b, R2c, SA3a, SA3b).

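### The missing-data rule for binary secondary outcomes contradicts itself when the event is unfavourable (all-cause discontinuation, use of ICP-lowering drugs)

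*Protocol*

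**What the plan says.** Section 16.2.1 reports the primary outcome as n/N, where "n is the number of participants with resolution of papilloedema and N the total number of participants in the corresponding trial arm". For participants without a primary outcome, section 16.2.4 says "they shall be treated as a failure and included in the denominator only and thus no imputation of missing data is planned". It extends this with no exception: "An analogous strategy for binary secondary outcomes will be used". Section 16.2.2 does the same for the comparison itself: "Binary outcomes will be compared using an analogous method to that described under the primary outcome".

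The secondary outcomes in section 8.1.2 include one plainly binary outcome with a favourable event, the headache responder rate, which section 8.2.4 says "is the proportion of participants achieving at least 50% reduction in the number of MHD". They also include two items whose event is unfavourable:

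- "Tolerability of weight loss in IIH driven by Tirzepatide as determined by all cause discontinuation at 6, 12 and 18 months"
- "Medication use (use and dose of acetazolamide or other ICP lowering drugs"), of which the use component is yes/no and the dose component is not.

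The protocol does not label either item as binary. Discontinuation is yes/no by nature, however, and section 6.5.1 already codes baseline acetazolamide as yes/no for minimisation.

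**The concern.** For resolution of papilloedema, being a failure and being absent from the numerator are the same thing, so the two halves of the rule give one coding. When the event counted in the numerator is a bad one, they give opposite codings. A participant in the denominator only is scored as not having discontinued, or as not using an ICP-lowering drug. A participant treated as a failure is scored as having discontinued, or as using the drug, and so belongs in the numerator. Both cannot be followed, and the protocol does not say which governs.

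At stake are the reported tolerability of Tirzepatide and the between-arm comparison of ICP-drug use. The trial is unblinded (section 6.6), so unequal loss between arms is plausible, and it would then feed directly into the ICP-drug comparison.

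**Working it through.** **Inputs from the protocol (section 16.1).** Type I error 0.05, power 90%, rates 5% and 37%, attrition 25%, 43 per arm. The protocol gives no event rate for discontinuation or ICP-drug use, so those below are assumptions shown over a range.

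**The plan's own figure.** With two-sided 0.05 (sidedness is not stated), pooled variance and no continuity correction:

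n = [1.960·√(2·0.21·0.79) + 1.282·√(0.05·0.95 + 0.37·0.63)]² / 0.32² ≈ 31.9, so 32 per arm. Then 32/0.75 = 42.7, so 43 per arm and 86 in total. The plan's figures reproduce. At the planned attrition, 32 of 43 are observed and 11 are missing.

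**The two readings.** Let p be the event rate among observed participants and m the missing fraction.

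- Denominator only: p(1−m).
- Missing scored as failure, event unfavourable: p(1−m) + m.
- Gap between the readings: m, whatever the value of p.

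For a favourable event both readings give p(1−m), so there is no conflict.

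**One arm of 43, with 32 observed and 11 missing:**

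| Observed events (assumed) | Observed rate | Denominator only | Missing as failure |
|---|---|---|---|
| 3/32 | 9.4% | 3/43 = 7.0% | 14/43 = 32.6% |
| 6/32 | 18.8% | 6/43 = 14.0% | 17/43 = 39.5% |
| 10/32 | 31.3% | 10/43 = 23.3% | 21/43 = 48.8% |
| 16/32 | 50.0% | 16/43 = 37.2% | 27/43 = 62.8% |

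The gap is 11/43 = 25.6 points in every row. With 10% missing it is 10 points: an observed 20% becomes 18% or 28%.

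**Arm contrast for ICP-drug use.** Suppose the same rate p in both arms, missingness unrelated to drug use, and missing fractions mT (Tirzepatide) and mS (standard of care). The true difference is 0. The calculated difference, Tirzepatide minus standard of care, is:

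- Denominator only: p(mS − mT).
- Missing as failure: −(1−p)(mS − mT).

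With p = 0.40, mT = 0.15 and mS = 0.35:

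- Denominator only: 0.40·0.85 − 0.40·0.65 = 0.34 − 0.26 = +8 points.
- Missing as failure: (0.34 + 0.15) − (0.26 + 0.35) = 0.49 − 0.61 = −12 points.

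With the same losses, p = 0.20 gives +4 or −16 points and p = 0.60 gives +12 or −8. If the losses are reversed, all signs reverse. If they are equal, the false difference is 0 under both readings, but each arm's rate is still distorted.

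**The case against.** Three arguments weigh against the point.

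First, a reader might infer that the rule makes both rates too low. The documents do not support that. Denominator-only counting does lower them, but the same sentence also says failure, and applying that half by analogy raises them. What is established is a contradiction with no stated resolution.

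Second, a reader might apply the full 25 points to discontinuation. That also goes too far. The 25% is attrition for the primary outcome, and a missing month-6 OCT does not make treatment status unknown. Declared changes in participation are recorded with date, reason and category on the Change of Status Form (section 11). Repeat prescriptions require a completed monthly visit (section 7.4), and pens are inspected monthly (section 7.5). Much of discontinuation is therefore knowable without any missing-data rule. Part of the concern remains: both categories in section 11 rest on a wish the participant expresses, so silent loss has no category. Someone who simply stops attending receives no further trial prescription, yet denominator-only counting would score that person as continuing.

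Third, section 16.2 is a brief outline, details are deferred to a SAP that is not shown, and neither outcome is labelled binary. That is fair for coding detail. But the protocol has already fixed a rule for every binary secondary outcome. A SAP that follows it inherits the conflict, and one that does not departs from the protocol. For ICP-drug use, moreover, choosing either half does not cure the distortion.

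**Conclusion.** The point holds as an internal contradiction that should be corrected. The rule in section 16.2.4 works only for binary outcomes whose event is favourable. For all-cause discontinuation and yes/no ICP-drug use, its two halves give rates that differ by the fraction with unknown status. That is at most about 25 points if the whole planned attrition had unknown status, and less for discontinuation because declared withdrawals are on record. For ICP-drug use, unequal loss creates a false arm difference whose size and sign depend on the reading.

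Only the 25% and the 43 per arm come from the protocol. The use rate, the 15% v 35% split and missingness unrelated to drug use are assumptions. So is the analysis of these two items as binary, although that is their natural form. The primary outcome and the headache responder rate are not affected by this contradiction.

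**What to change.** In section 16.2.4, and correspondingly in the SAP:

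- Limit missing-as-failure to binary outcomes whose event is favourable, such as headache response.
- Derive all-cause discontinuation from the change-of-status, prescription and visit records. Count a participant who is lost, or withdrawn from treatment, before the time point as discontinued.
- Do not apply the rule to ICP-drug use. Use the concomitant-medication records collected at each monthly visit (section 9.3 and Table 1 in section 10), either in an observed-data analysis or in a model for the repeated records. Report the number still missing by arm.

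The cost is one paragraph of text and slightly more analysis work; no new data are needed. The reported discontinuation rate may be less favourable. The ICP-drug analysis will rest on an assumption about the missing records, which should be stated.

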16.3. Planned final analyses

Final analyses will take place once the last randomised participant has reached the primary 18 month endpoint and corresponding outcome data has been entered onto the trial database and validated as being ready for analysis.

17. Exploratory research sample sub-study

Full details of blood, saliva, urine, and stool sample processing are described in the trial laboratory manual.

17.1. Sample collection

Before baseline, 3 month, and 6 month appointments, a sample kit will be posted to participants. This will consist of separate kits for:

- Blood – a capillary blood sampling kit will be provided for the collection of approximately 0.5ml of blood for processing into plasma, and another for approximately 0.5ml of blood for processing into serum. Participants will be requested to fast from midnight (water only) on the day of sample collection.
- Saliva – a swab and prepared tube will be provided for the collection of approximately 1 swab of saliva and 2ml of saliva drool. Participants will be requested to fast from midnight (water only) on the day of sample collection. Participants will also be requested to provide a saliva sample on a day they self-rate as a severe headache day, and another on a good headache day.
- Urine – a kit will be provided for a 24-hour urine collection, of which approximately 20ml of urine will then be sampled and collected for trial use.
- Stool – a kit will be provided for the collection of approximately 1g of stool.

Kits will include secure postage containers to send the samples to the UoB Biomedical Sciences Laboratory.

17.2. Sample labelling

The sample kit sent to participants will be sent with a partially pre-completed set of sample labels coded with trial number, sample type, and timepoint, with the date to be completed by the participant prior to attaching to the sample container.

17.3. Sample handling and storage

Once received in the laboratory, samples will be processed as below before storage:

- Bloods - the microtainers will be centrifuged and the resulting supernatant designated plasma or serum. Following centrifugation, plasma/serum will be divided into aliquots, labelled and stored in the laboratory's -80 freezer.
- Saliva – the saliva will be divided into aliquots, labelled and stored in the laboratory's -80 freezer.
- Urine – the urine will be divided into aliquots, labelled and stored in a -20 freezer.
- Stool - the stool sample will be homogenized and the resulting homogenate centrifuged, and the supernatant stored in the laboratory's -80 freezer.

After all trial analysis is complete, the samples will be destroyed.

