3.3. Sub-studies

- A mechanistic sub-study will collect biofluids (saliva, blood, 24-hour urine and stool) for evaluation of weight-loss related changes in liver function, diabetic status, hormones, markers of inflammation, pain chemicals involved in headache, and microRNA. Stool samples will be collected to evaluate the gut microbiome. Samples will be collected at baseline, 3 and 6 months. Please see **section 17** for full details.
- A qualitative sub-study will conduct two focus group discussions with main trial participants to explore acceptability of weight management strategies and the experience of people living with IIH and their weight management discussions with healthcare professionals. Please see **section 18** for full details.
- A sleep sub-study will use a wearable device to explore IIH, weight loss, and the circadian cycle and daytime activity.

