8.1.3. Exploratory outcomes

All exploratory outcomes measured at 12 and 18 months from baseline unless stated otherwise and assessed in a subset of participants:

- Clinical outcomes:
 - Resolution of papilloedema as measured by OCT
 - Change in papilloedema as measured by OCT
 - Headache: Monthly headache days, Monthly migraine days, Headache responder rate ($\geq 50\%$ reduction in MHD), Monthly analgesic days and Monthly headache severity (numerical rating scale lowest 0-10 highest).
 - Headache disability (using the HIT-6)
 - Weight and BMI
- Patient-centred outcomes:
 - Quality of life (QoL) measured using the SF-36 summary score, physical component score and mental component score
 - QoL measured using the EQ-5D-5L
 - Vision related QoL measured using the NEI-VFQ-25 plus the 10-item supplement
 - Binge eating measured using the BES
 - Alcohol use measured using the AUDIT
 - Anxiety and depression measured using the HADS
- Economic outcomes:
 - Service use (doctor attendance, hospital attendance, days in hospital, lumbar punctures, brain imaging scans) (as recorded by CSRI)
 - Medication use (use and dose of acetazolamide or other ICP lowering drugs)

- Absenteeism and presenteeism measured using the WPAI
- Sleep outcomes:
 - Sleep, circadian cycle and daytime activity will be evaluated at baseline, 3 and 6 months using wearable device actigraphy data and the Pittsburgh Sleep Quality Index, Insomnia Severity Index, Berlin questionnaire and STOP-Bang sleep apnoea screening questionnaire

Exploratory mechanistic outcomes

- Blood, saliva, 24-hour urine and stool samples will be collected at baseline, 3 and 6 months for later analysis for miRNA biomarkers, steroid metabolomics, protein biomarkers, inflammatory markers and Calcitonin Gene-Related Peptide, and rRNA sequencing to analyse gut microbiome changes.

Exploratory sleep sub-study outcomes

- Sleep, circadian cycle and daytime activity will be evaluated at baseline, 3 and 6 months.

Qualitative sub-study outcomes

A qualitative sub-study will answer the following research questions:

- What is the experience of weight management services and strategies for people with IIH?
- What should an optimal IIH weight management service look like?

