17.4. Provisional sample processing

The provisional downstream processing planned may include:

- Real time Polymerase Chain Reaction – serum and saliva swabs for changes in miRNA biomarkers related to IIH and weight change.

- Mass spectrometry – urine and serum for steroid metabolomics related to IIH and weight change.
- ELISA/O-link – plasma and saliva drool analysed for protein biomarkers, inflammatory markers related to IIH and weight change, and calcitonin gene-related peptide.
- 16s rRNA sequencing – to analyse gut microbiome changes with relation to weight change and with correlation to clinical outcomes.

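### Only the supernatant of centrifuged stool is listed for storage, although the one stool analysis named, 16S rRNA sequencing, needs bacterial cells or their DNA

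*Protocol*

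**What the plan says.** Section 3.3 gives one purpose for the stool: "Stool samples will be collected to evaluate the gut microbiome". Section 8.1.3 makes this an exploratory mechanistic outcome, from samples at baseline, 3 and 6 months, by "rRNA sequencing to analyse gut microbiome changes". Section 17.1 sets the quantity: "a kit will be provided for the collection of approximately 1g of stool". It describes no second tube.

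Section 17.3 puts processing ahead of freezing ("samples will be processed as below before storage"), and for stool this means that the sample is homogenised, "the resulting homogenate centrifuged, and the supernatant stored" at -80. Saliva and urine are only divided into aliquots and labelled before freezing, without a spin.

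Section 17.4 opens with "The provisional downstream processing planned may include" and lists four laboratory methods. The last is 16S rRNA sequencing, "to analyse gut microbiome changes with relation to weight change and with correlation to clinical outcomes". That entry does not say which fraction of the stool is used. The opening of section 17 refers full processing details for all four sample types to the trial laboratory manual.

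**The concern.** 16S sequencing reads a bacterial gene, and in fresh stool most of that DNA lies inside intact cells. Spinning a homogenate and keeping the liquid is the usual handling for soluble analytes, and section 17.4 plans no soluble stool analyte. The one fraction listed for storage is therefore not the obvious one for the one analysis listed.

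If the spin sediments intact bacteria, the stored tube holds less bacterial DNA, and what remains leans towards free DNA and whatever did not sediment. Composition would then depend partly on spin conditions, which adds noise or bias to the within-person change that the outcome is meant to measure. A baseline sample cannot be collected again once treatment has begun. Section 5.7 does not make the sample sub-study optional, so every participant is asked for stool.

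**Working it through.** The plan gives no figure to reproduce. The check has two parts.

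**1. Stored fraction against planned use**

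| Method in 17.4 | Specimen named |
|---|---|
| Real-time PCR | serum, saliva swab |
| Mass spectrometry | urine, serum |
| ELISA/O-link | plasma, saliva drool |
| 16S rRNA sequencing | none named; the gut microbiome target implies stool |

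Stool appears in no method except, by implication, the last. Section 17.3 lists one stored stool fraction, the supernatant. So the only stored fraction has to serve the 16S assay, and nothing in the protocol says how bacterial material stays in it.

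**2. Would an ordinary spin remove the bacteria?**

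None of the inputs is in the protocol. All are assumptions: intact cells of diameter d = 1 micron; density excess of 50 to 100 kg/m3; water viscosity, 0.001 Pa s; settling depth 3 cm.

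Settling speed is v = d² × density excess × RCF × 9.81 / (18 × viscosity). The time to clear the column is 0.03 m / v.

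Example at 1,000 g and 50 kg/m3: v = 10⁻¹² × 50 × 1,000 × 9.81 / (18 × 0.001) = 2.725 × 10⁻⁵ m/s. The time is 0.03 / (2.725 × 10⁻⁵) = 1,101 s, or 18.3 min. Doubling the density excess halves this to 9.2 min. Time is inversely proportional to speed:

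| RCF | Time to clear 3 cm (100 to 50 kg/m3) |
|---|---|
| 200 g | 46 to 92 min |
| 1,000 g | 9 to 18 min |
| 3,000 g | 3 to 6 min |
| 10,000 g | 1 to 2 min |

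Speed alone does not settle the matter. For cells evenly suspended at the start, the share removed is roughly spin time divided by clearing time:

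- 5 min at 1,000 g: 5/18.3 = 27% to 5/9.2 = 54%.
- 1 min at 3,000 g: 1/6.1 = 16% to 1/3.06 = 33%.
- 10 min at 1,000 g: 10/18.3 = 55%, up to all of them (10 min exceeds 9.2 min).

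On these assumptions the supernatant could hold most of the intact cells or almost none, depending on settings that the protocol does not give. If homogenisation lyses the cells, the calculation does not apply, because the released DNA would largely stay in the liquid.

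**Number of samples.** Taking the three time points in sections 3.3, 8.1.3 and 17.1 and full attendance: 86 × 3 = 258.

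**The case against.** The strongest reply is that section 17.3 is a short summary and the detail sits in the laboratory manual. A lysing homogenisation followed by a clearing spin would make the supernatant a suitable input for 16S work. A brief or slow spin would leave many bacteria in suspension. The settling times rest on assumed values, use water viscosity for a faecal suspension, and presuppose intact cells. The list in 17.4 is provisional, and 17.5 foresees transfer of samples to a biobank for other research, so 17.4 need not name every use.

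Much of this stands. A reader might infer that the pellet is thrown away, that the microbiome outcome therefore cannot be measured, and that the loss could never be put right. The protocol supports none of these: it is silent on the pellet, on spin settings and on lysis. Nor does 258 mean 258 compromised samples; it is the most that the handling rule could touch.

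The reply does not remove the point. Section 17.3 does more than omit detail, because it names the fraction to be kept. A manual that kept whole stool or pellet in its place would depart from the protocol's wording. And while 17.4 is provisional, 8.1.3 lists the sequencing outcome without that reservation.

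**Conclusion.** The point holds in a limited form. As written, the only stool fraction listed for storage may be depleted of, or biased for, the material that the only named stool analysis needs, and the protocol does not say how bacterial material is retained. Whether harm follows depends on three things not stated: whether homogenisation lyses the cells, how hard and how long the spin is, and what becomes of the pellet. The laboratory manual may answer all three.

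The reach is one component of an exploratory mechanistic outcome. The primary and secondary outcomes, sample size and error rates are untouched. I rate it a cheap improvement, with moderate confidence because the manual is not available.

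**What to change.** In section 17.3, and in the same terms in the laboratory manual, state that an aliquot of whole stool or uncentrifuged homogenate (or the pellet) is stored at -80 for 16S sequencing. Supernatant can be kept as an additional aliquot if wanted. Whole stool or uncentrifuged homogenate is the safer choice, since it serves whether or not homogenisation lyses the cells; a pellet alone would not. In section 17.4, name the fraction that feeds the 16S assay, as the other three entries already do.

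If the supernatant is intended, the lesser remedy is to state the lysis step or spin conditions that make it suitable and to hold them constant across samples.

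The cost is one extra cryovial and freezer space per sample, up to 258, and a division of the roughly 1 g collected. No visit or participant task is added. The change is worth making before baseline samples are processed.
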